## 9.2 Clinical Laboratory Tests

### 9.2.1 Change from Baseline in Lab Tests

Summary statistics for mean and mean change from baseline in the routine clinical laboratory measurements, prolactin concentrations, coagulation parameters (PT, aPTT, and INR), HbA1c, cortisol, ACTH, and TSH will be provided by treatment and by visit.

### 9.2.2 Potentially Clinically Relevant Values

In addition, the incidence of treatment-emergent potentially clinically relevant (PCR) values identified using prospectively defined criteria in Appendix 1 for laboratory tests will be summarized by treatment group. A listing of PCRs by subject and by test will be provided.

### 9.2.3 Potentially Liver Injury Related Laboratory Test

Total bilirubin level will be checked for any subjects with increased ALT or AST levels greater or equal to three times the upper normal limits (or baseline).

Liver injury related laboratory test results will be summarized for subjects who met following criteria. The corresponding listing will be provided as well.

- AST or ALT  $\geq 3 \times$  ULN and
- T\_Bili  $\geq 2 \times$  ULN

### 9.2.4 Metabolic Change

In addition to mean change from baseline, the incidence of treatment emergent significant changes in fasting lipids, fasting glucose, and metabolic syndrome will be summarized by treatment group using the following criteria.

Criteria for Treatment-Emergent Significant Change in Lipids and Glucose		
LAB PARAMETER	BASELINE*	ANYTIME POST BASELINE
LDL Direct, Fasting (MG/DL)	Borderline 100-<160 Normal/Borderline <160 Normal <100 Any Value	High $\geq 160$ High $\geq 160$ Borderline/High $\geq 100$ Increased $\geq 30$

Criteria for Treatment-Emergent Significant Change in Lipids and Glucose		
LAB PARAMETER	BASELINE*	ANYTIME POST BASELINE
HDL Cholesterol, Fasting (MG/DL)	Normal $\geq 40$ Any Value	Low $< 40$ Decreased $\geq 20$
Triglycerides, Fasting (MG/DL)	Normal $< 150$ Borderline 150- $< 200$ Normal/Borderline $< 200$ Normal $< 150$ Any Value	High 200- $< 500$ High 200- $< 500$ High 200- $< 500$ Borderline/High/Very High $\geq 150$ Increased $\geq 50$
Glucose Fasting, Serum (MG/DL)	Normal $< 100$ Impaired 100- $< 126$ Normal/Impaired $< 126$ Any Value	High $\geq 126$ High $\geq 126$ High $\geq 126$ Increased $\geq 10$

\* Baseline is calculated from day 0; if day 0 is unavailable screen visit will be used

Criteria for Treatment-Emergent Metabolic Syndrome	
DESCRIPTION	ANYTIME POST BASELINE*
Central Obesity	Waist Circumference $\geq 102$ cm(MALE), $\geq 88$ cm (FEMALE)
Dyslipidemia	Triglycerides $\geq 150$ mg/dl
Dyslipidemia	HDL $< 40$ mg/dl (MALE), $< 50$ mg/dl (FEMALE)
Supine Blood Pressure	Systolic $\geq 130$ mmHg and Diastolic $\geq 85$ mmHg
Glucose Fasting, Serum	$\geq 100$ mg/dl
Metabolic Syndrome	Met 3 Or More of the Above Criteria at a Visit

\* Baseline is calculated from day 0; if day 0 is unavailable screen visit will be used

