8.	Subjects who currently have clinically significant neurological, hepatic, renal, metabolic, hematological, immunological, cardiovascular, pulmonary, gastrointestinal, or psychiatric disorders. Clinically significant cardiovascular disorders include uncontrolled atrial fibrillation, heart failure, or ischemic heart disease. Surrogates for uncontrolled cardiovascular disease would include recent (within the last 6 months) hospitalizations or procedures, such as percutaneous coronary intervention, coronary bypass surgery. 
Medical conditions that are minor or well-controlled may be considered acceptable if the condition does not expose the subject to an undue risk of a significant adverse event or interfere with assessments of safety or efficacy during the course of the trial. The medical monitor should be contacted in any instance where the investigator is uncertain regarding the stability of a subject's medical condition(s) and the potential impact of the condition(s) on trial participation.

Protocol 331-12-284

Table 3.4.3-1 Exclusion Criteria	
9.	Subjects with uncontrolled hypertension (DBP > 95 mmHg) or symptomatic hypotension, or orthostatic hypotension, which is defined as a decrease of $\geq 30$ mmHg in SBP and/or a decrease of $\geq 20$ mmHg in DBP within 3 minutes of standing compared to the previous supine blood pressure, OR development of symptoms. Abnormal vital signs results should be repeated to ensure reproducibility of the abnormality before excluding a subject based on the criteria noted above.

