## Appendix 2                      Criteria for Identifying Vital Signs of Potential Clinical Relevance

Variable	Criterion Value a	Change Relative to Baseline a
Heart Rate b	> 120 bpm < 50 bpm	≥ 15 bpm increase ≥ 15 bpm decrease
Systolic Blood Pressure b	> 180 mmHg < 90 mmHg	≥ 20 mmHg increase ≥ 20 mmHg decrease
Diastolic Blood Pressure b	> 105 mmHg < 50 mmHg	≥ 15 mmHg increase ≥ 15 mmHg decrease
Orthostatic Hypotension	≥ 20 mmHg decrease in systolic blood pressure and a ≥ 25 bpm increase in heart rate from supine to sitting/standing	Not Applicable (baseline status not considered)
Weight	-	≥ 7% increase ≥ 7% decrease

a In order to be identified as potentially clinically relevant, an on-treatment value must meet the “Criterion Value” and also represent a change from the subject’s baseline value of at least the magnitude shown in the “Change Relative to Baseline” column.

b As defined in “Supplementary Suggestions for Preparing an Integrated Summary of Safety Information in an Original NDA Submission and for Organizing Information in Periodic Safety Updates,” FDA Division of Neuropharmacological Drug Products draft (2/27/87).

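### The metabolic-syndrome table scores blood pressure only when systolic and diastolic limits are both met, so elevation of one pressure alone never counts (minor)

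*SAP*

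**What the plan says.** SAP 9.2.4 states that the incidence of significant changes in fasting lipids, fasting glucose and "metabolic syndrome will be summarized by treatment group using the following criteria". The metabolic-syndrome table lists five components: waist circumference, triglycerides, HDL, supine blood pressure and fasting glucose. The blood-pressure row reads "Systolic $\geq 130$ mmHg and Diastolic $\geq 85$ mmHg". The syndrome row reads "Met 3 Or More of the Above Criteria at a Visit". The only criterion column refers to any time after baseline. A footnote says how baseline is chosen, but the table has no baseline column.

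The plan treats the two pressures differently elsewhere:
- **SAP Appendix 2 (also Protocol Appendix 4).** Systolic pressure ("> 180 mmHg < 90 mmHg") and diastolic pressure ("> 105 mmHg < 50 mmHg") have separate rows. Neither requires the other, though each also requires a stated change from baseline.
- **Protocol 3.4.3, exclusion 9.** Uncontrolled hypertension is set on diastolic pressure alone: "Subjects with uncontrolled hypertension (DBP > 95 mmHg) or symptomatic hypotension". The postural-fall limb of the same criterion joins systolic and diastolic falls with *and/or*.
- **The metabolic-syndrome table itself.** Triglycerides and HDL are separate rows, and each scores on its own.

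**The concern.** Blood pressure is the only row of the five that needs two abnormal readings to score one component. Subjects are aged 55 to 90, and no numeric entry limit bars a systolic pressure of 130 mmHg or more with a diastolic pressure below 85 mmHg. Such a subject with two other components is reported as not having the syndrome. The same holds for a subject with only diastolic pressure raised.

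Safety and tolerability form the trial's stated secondary objective. Protocol 1.3 reports statistically significant weight increases on brexpiprazole in earlier populations, so a metabolic summary is a relevant output. A rule that drops cases in both arms shrinks the event count on which the arms are compared descriptively.

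**Working it through.** The plan states no metabolic-syndrome rate, so there is no figure to reproduce. The check has two parts: the direction of the effect, which needs no data, and its size, which rests on assumptions.

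**1. Direction: enumerate the patterns.** At Week 12 all five components can be measured. The four components other than blood pressure give 2^4 = 16 combinations. Blood pressure has four states (neither raised, systolic only, diastolic only, both), so there are 16 × 4 = 64 patterns.
- The two rules disagree only when exactly one pressure is raised (2 states) and exactly two other components are present (C(4,2) = 6 combinations). That is 6 × 2 = 12 patterns, of which 6 are systolic only.
- The either/or rule adds the syndrome in all 12 and removes it in none.
- With three or four other components the subject is counted under both rules. With none or one, under neither.

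Protocol 3.7.4.3.1 schedules waist circumference only at screening and Week 12/ET. At Weeks 4 and 8 there are three other components, so 8 × 4 = 32 patterns. The rules disagree in C(3,2) × 2 = 6 (3 of them systolic only), again with none removed.

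**2. Size at Week 12, on assumed inputs.** The documents give no prevalences. Assume:
- each of the four other components is present independently with probability p, from 0.20 to 0.50;
- both pressures are raised in 10% to 15% of subjects (B);
- exactly one pressure is raised in 20% to 40% (S), independently of the other components.

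Formulas:
- exactly two others: E = 6 p²(1−p)²
- three or more others: T = 4 p³(1−p) + p⁴
- *and* rule: T + E·B
- either/or rule: T + E·(B + S)
- missed: E·S

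Low end, p = 0.20, B = 0.10, S = 0.20: E = 6 × 0.04 × 0.64 = 0.1536; T = 0.0256 + 0.0016 = 0.0272. The *and* rule gives 0.0272 + 0.0154 = 0.0426 and either/or gives 0.0272 + 0.0461 = 0.0733. Missed: 0.1536 × 0.20 = 0.0307.

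High end, p = 0.50, B = 0.15, S = 0.40: E = 0.375; T = 0.3125. The *and* rule gives 0.3688 and either/or gives 0.5188. Missed: 0.375 × 0.40 = 0.150.

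| p | B | S | *and* rule | either/or | missed (points) | of 130 per arm | share of either/or cases missed |
|---|---|---|---|---|---|---|---|
| 0.20 | 0.10 | 0.20 | 4.3% | 7.3% | 3.1 | 4.0 | 42% |
| 0.20 | 0.15 | 0.40 | 5.0% | 11.2% | 6.1 | 8.0 | 55% |
| 0.30 | 0.10 | 0.30 | 11.0% | 19.0% | 7.9 | 10.3 | 42% |
| 0.40 | 0.10 | 0.30 | 21.4% | 31.7% | 10.4 | 13.5 | 33% |
| 0.50 | 0.10 | 0.20 | 35.0% | 42.5% | 7.5 | 9.8 | 18% |
| 0.50 | 0.15 | 0.40 | 36.9% | 51.9% | 15.0 | 19.5 | 29% |

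The per-arm counts use the planned 130 randomized and suppose that all have Week 12 data.

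**The case against.** **No reference definition.** The SAP cites no source for its criteria, so an under-count can only be claimed relative to an either/or rule. This stands. The comparison rests on the plan's own handling of blood pressure, and that support is imperfect. Appendix 2 is a screen for extreme values with an added change requirement, and exclusion 9 concerns eligibility. The SAP also uses conjunctions elsewhere: transaminase with bilirubin in 9.2.3, and a systolic fall with a heart-rate rise for orthostatic hypotension in Appendix 2. Those pair different measurements to define one event, but they show that *and* is not in itself proof of a slip.

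**Direction under new onset.** If treatment-emergent means absent at baseline, as the QT table in SAP 9.4 defines new onset, the either/or rule also adds subjects who already qualify at baseline. Take a subject with two other components whose systolic pressure is already at or above 130 mmHg at baseline and whose diastolic pressure later reaches 85 mmHg. That subject is newly emergent under *and*, but not under *or*. This stands: the certain direction holds only for the table as written.

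**Low consequence.** The table is descriptive, the rule is identical in both arms, and vital signs, weight, lipids and glucose are summarized separately. This also stands and keeps the severity low.

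**Stronger readings that the documents do not support.**
- A reader might infer that the share of older subjects with isolated systolic elevation is the share of syndrome cases lost. The documents give no blood-pressure data, and failing one component changes the syndrome count only with exactly two others present.
- A reader might take a subject with high systolic pressure throughout the trial as the typical missed case. That subject's raised pressure predates treatment and says little about emergence.
- A reader might argue that the diastolic entry limit makes the row depend on a truncated measurement. The limit of 95 mmHg is well above 85 mmHg. Exclusion 18 and Protocol 3.7.4.3.3 also exclude other medically significant vital signs at screening, so diastolic pressure is not the only one controlled.

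**Conclusion.** The point holds and is minor. As written, elevation of one pressure alone can never meet the blood-pressure component. On the table's own any-time-after-baseline wording, this can only reduce the syndrome count relative to an either/or rule, and only among subjects with exactly two other components.

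The shortfall of about 3 to 15 percentage points at Week 12 (18% to 55% of the cases an either/or rule would count) depends entirely on assumed prevalences and on independence between components, which real lipid, glucose and waist data may not satisfy. It illustrates scale and does not estimate this trial's rate. It applies in both arms. The documents give no ground for inferring a biased treatment comparison or any effect on the CMAI or CGI-S results.

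**What to change.** In SAP 9.2.4, change the blood-pressure row to: Systolic >= 130 mmHg or Diastolic >= 85 mmHg. Leave the other rows as they are. If *and* is deliberate, name the source definition and report the either/or count beside it.

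The cost is one word in the SAP and one line of code, or one extra table row under the alternative. No new data are needed. The change should be made before unblinding. The downside is that the reported incidence will generally be higher in both arms. If new onset relative to baseline is intended, the change could be smaller, because more subjects would already qualify at baseline. The SAP should say which of the two meanings applies.

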### 9.3 Physical and Neurological Examination and Vital Signs

Physical and neurological examination findings will be listed by subject.

Summary statistics for change from baseline in vital signs, body weight, and waist circumference will be provided by treatment group.

In addition, the incidence of treatment-emergent PCR values identified using prospectively defined criteria in Appendix 2 for vital signs and body weight will be summarized by treatment group. Listing of PCRs by subject and by test will be provided.

### 9.4 12-Lead ECG

Summary statistics for change from baseline in ECG parameters will be provided by treatment and by visit.

In addition, the incidence of treatment-emergent potentially clinically relevant (PCR) values identified using prospectively defined criteria for ECG will be summarized by treatment group. Listing of PCRs by subject and by test will be provided.

For the analysis of QT and QTc, data from three consecutive complexes (representing three consecutive heart beats) will be measured to determine average values. The following QT corrections will be used for reporting purposes in the clinical study report:

- 1) QTcB is the length of the QT interval corrected for heart rate by the Bazett formula:  $QTcB = QT / (RR)^{0.5}$  and
- 2) QTcF is the length of the QT interval corrected for heart rate by the Fridericia formula:  $QTcF = QT / (RR)^{0.33}$
- 3) QTcN is the length of the QT interval corrected for heart rate by the FDA Neuropharm Division formula:  $QTcN = QT / (RR)^{0.37}$

Categorical changes in ECG parameters during the double blind treatment period will be summarized based on the following criteria:

Categorical Change Criteria in QT/QTc Parameters		
Classification	Category	Criteria
QT	New Onset ( $\geq 450$ Msec for men or $\geq 470$ Msec for women)	New onset in QT means a subject who attains a cut off value during treatment period but not at baseline.
QTc *	New Onset ( $\geq 450$ Msec for men or $\geq 470$ Msec for women)	New onset in QTc means a subject who attains a cut-off value during treatment period but not at baseline.
	New Onset ( $\geq 450$ Msec for men or $\geq 470$ Msec for women) And $> 10\%$ Increase	New onset and $> 10\%$ increase in QTc means a subject who attains a cut off value and $> 10\%$ increase during treatment period but not at baseline
	New Onset ( $> 500$ Msec)	New onset ( $> 500$ msec) in QTc means a subject who attains a value $> 500$ msec during treatment period but not at baseline.
	Increase 30 - 60 Msec	Increase from baseline value $> 30$ and $\leq 60$ msec in QTc
	Increase $> 60$ Msec	Increase from baseline value $> 60$ msec in QTc

\* QTc categorical change criteria apply to QTcB, QTcF and QTcN.

## 9.5 Body Weight, Waist Circumference and Body Mass Index (BMI)

Analyses of body weight, waist circumference and BMI will be performed for the Safety Sample. Body mass index is defined as weight in kilograms divided by the square of height in meters. The mean change from baseline to Week 12 (OC) and the last visit in the double blind treatment period in body weight will be tabulated and analyzed using ANCOVA. The ANCOVA models will include the baseline as a covariate and the treatment group as fixed effect.

Percentages of subjects showing significant weight gain ( $\geq 7\%$  increase in weight), as well as percentages of subjects showing significant weight loss ( $\geq 7\%$  decrease in weight) from baseline to Week 12 (OC and LOCF) will be analyzed using Cochran-Mantel-Haenszel (CMH) General Association Test.

**9.6** CCI [REDACTED]

[REDACTED]

**9.7 Mini-Mental State Examination (MMSE)**

The mean changes from baseline to Week 12 (OC) and the last visit in the double blind treatment period in MMSE will be tabulated and analyzed by treatment group using ANCOVA. The ANCOVA model for the OC data set will include the baseline item score as covariate and treatment group as main effect. The ANCOVA model for last visit will include the baseline item score as covariate, and study center, treatment group as main effects. The analyses will be performed for Safety Sample.

**9.8** CCI [REDACTED]

[REDACTED]

## 9.9 Concomitant Medications

Number and proportion of subjects taking concomitant medications prior to study therapy, during the double blind treatment period, and after study therapy are tabulated by drug classification using the WHO drug dictionary.

## 9.10 Extent of Exposure

The start date of double-blind study therapy - brexpiprazole or placebo - will be the first day of double-blind dosing. The number and percentage of subjects, who receive double-blind study medication, will be presented by week and by treatment group. Each dosing week will be based on the actual week; i.e., Day 1-7 in Week 1, Day 8-14 in Week 2, etc. This summary will be performed on the Safety Sample.

The number and percentage of completers will be presented by week and by treatment group.

The mean daily dosage will be summarized by week and treatment group using descriptive statistics. The mean daily dosage per subject per week will be determined for each week of the study. This will be calculated by dividing the sum of individual total doses by the number of days in the week interval. The summary will contain for each treatment group the number of subjects receiving double-blind study medication, and the mean and range of the mean daily dose for each week.

The number and percentage of subjects will be presented by modal dose, by final dose and by treatment group.

## 10 Conventions

### 10.1 Study Visit Windows

Study visit windows will be used to map visits using study day intervals. This visit window convention applies to tables and listings for all efficacy and safety scales. In listings it will be listed along with the CRF study visit.

Table below shows classifications for study day intervals in the double-blind period. The variable “target day” is defined using the number of days since the start of double-blind

dosing. The first day of double-blind dosing is defined as “Day 1”. If more than one observation falls within a particular study day interval, then the last observation within that interval is used. CCI [REDACTED]

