### **3.5. Outcome Variables**

#### **3.5.1. Primary Efficacy Variable**

The primary efficacy variable is the change from baseline to Week 12/ET in the CMAI total score. The primary analysis will use a mixed-effect model repeated measure (MMRM) approach.

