The investigator will notify the sponsor promptly when a subject is withdrawn. Subjects withdrawn prior to Week 12 must complete the Week 12/ET evaluations at the time of withdrawal. In addition, all subjects who withdraw prematurely from the trial will be assessed 30 (+2) days after the last dose of the IMP for evaluation of safety. This assessment can be accomplished at a clinic visit at either the investigator's site or residential facility, if applicable. If a clinic visit is not possible, the subject should be assessed by telephone contact with the subject and a caregiver. CCI

Three attempts will be made to contact the subject's caregiver by telephone; in the event the site is unable to reach the subject's caregiver by telephone, the site will attempt to contact the subject's caregiver via certified mail or an alternative similar method where appropriate.

Any subject who withdraws prematurely from the trial will not be eligible to roll-over into Trial 331-13-211.

Protocol 331-12-284

Meeting a screening exclusion criterion postrandomization does not require an automatic discontinuation of the subject. The investigator should assess the change for clinical significance, determine if an AE should be reported, and make a determination of subject continuation based on subject safety. The investigator could consult with the medical monitor to determine subject continuation in the trial.

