#### **8.1.1 Primary Efficacy Analysis**

The primary endpoint will be analyzed using a mixed-effect model repeated measure (MMRM) model. The primary efficacy outcome measure is the mean change from baseline (Day 0 visit) to the end of the double-blind treatment period (Week 12 visit) in the CMAI total score. The primary statistical comparison of interest is brexpiprazole flexible dose versus placebo. The null hypothesis is that there is no difference between the brexpiprazole treatment group and placebo in change from baseline to endpoint in CMAI total score. The comparison will be made at the significance level of  $\alpha = 0.05$  (2-sided).

The primary analysis will be performed on the Efficacy Sample which includes all randomized subjects who took at least one dose of IMP in the double blind treatment period and who have both a baseline and at least one post-randomization CMAI Total Score during the double blind treatment period. The primary efficacy analysis will be performed by fitting a MMRM analysis with an unstructured (UN) variance covariance structure in which the change from the baseline in CMAI Total Score (Week 2, 4, 6, 8, 10, 12) will be the dependent variable based on the OC data set. The model will include fixed class-effect terms for treatment (brexpiprazole and placebo), trial center, visit week, and an interaction term of treatment by visit week and include the interaction term of baseline values of CMAI Total Score by visit week as covariates. The primary comparison between a brexpiprazole and the placebo arm at Week 12 will be estimated as

the difference between Least Squares (LS) means from the interaction term of treatment by visit week utilizing the computing software SAS procedure PROC MIXED.

CCI [Redacted]

[Redacted]

[Redacted]

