### Study Day and Visit Window

Week	Target Day a	Study Day Interval a
1	7	2-10
2	14	11-17
3	21	18-24
4	28	25-31
5	35	32-38
6	42	39-45
7	49	46-52
8	56	53-59
9	63	60-66
10	70	67-73
11	77	74-80
12	84	81-91 b

a Relative to the first day of IMP in the double blind treatment period.

CCI [REDACTED]

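### On the visible text of SAP 10.1, early-termination CMAI and CGI-S scores that fall in odd-week windows get a week label the primary MMRM does not use

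*SAP*

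**What the plan says.** - **Visit labels.** SAP 10.1: "Study visit windows will be used to map visits using study day intervals", and "This visit window convention applies to tables and listings for all efficacy and safety scales". The table has twelve consecutive windows, counted "Relative to the first day of IMP in the double blind treatment period". The odd weeks are Days 2-10, 18-24, 32-38, 46-52, 60-66 and 74-80. The even weeks are Days 11-17, 25-31, 39-45, 53-59, 67-73 and 81-91.
- **Several scores in one window.** "If more than one observation falls within a particular study day interval, then the last observation within that interval is used".
- **Primary model.** SAP 8.1.1: "the change from the baseline in CMAI Total Score (Week 2, 4, 6, 8, 10, 12) will be the dependent variable". It uses observed cases, and SAP 5.2 says nothing is imputed. SAP 8.2 applies the same method to CGI-S.
- **ET assessment.** Protocol 3.8.3: "Subjects withdrawn prior to Week 12 must complete the Week 12/ET evaluations at the time of withdrawal". Protocol 3.7.1.4 lists CMAI and CGI-S among those evaluations.
- **Efficacy Sample.** SAP 5.1 asks for a baseline and any one post-baseline CMAI total score, with no restriction on week.

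**The concern.** The CMAI and CGI-S are scheduled after baseline only at the even weeks. The odd-week windows therefore serve no scheduled efficacy visit, and the scores they catch are mainly ET scores. Whether such a score enters the primary analysis then depends on the calendar day of withdrawal and not on a stated choice.

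The ET score is the last value before dropout. Protocol 3.8.3 makes clinically significant agitation that allowed medication cannot control, and that poses a safety risk, a reason for mandatory withdrawal. Take a subject who worsens after the Week 4 visit and leaves on Day 35. The ET score records what drove the withdrawal. An MMRM under missing at random relies on dropout being explained by data in the model. If that score is left out, dropout depends on a value the model never sees.

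**Working it through.** **1. The plan's own figures.** The documents give no count of ET scores, no ET rate and no distribution of ET days. The nearest figure is the 10% non-evaluable allowance: 117 / (1 - 0.10) = 130 per arm, 260 in total, as stated. It is not an ET rate, and the sample size does not change here.

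**2. Scheduled visits against the windows.** Target day is 7 x week, with an allowance of 2 days either way (Protocol 3.7.1.3.2 and 3.7.1.4).

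| Visit | Allowed days | SAP window |
|---|---|---|
| Week 2 | 12-16 | 11-17 |
| Week 4 | 26-30 | 25-31 |
| Week 6 | 40-44 | 39-45 |
| Week 8 | 54-58 | 53-59 |
| Week 10 | 68-72 | 67-73 |
| Week 12 | 82-86 | 81-91 |

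Every on-time visit lands in its even-week window. Odd-week windows can receive only ET scores, unscheduled scores, or visits held outside the allowance.

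**3. Share of days.**
- Odd-week days: 9 + 7 + 7 + 7 + 7 + 7 = 44.
- Even-week days before Day 81: 5 x 7 = 35.
- Days 2-80: 44 / (44 + 35) = 44/79 = 55.7%.
- Days 11-80: 35/70 = 50.0%.
- Days 2-91, with the 11-day Week 12 window: 44/90 = 48.9%.

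**4. Share of scores.** Let q be the fraction of ET assessments that coincide with a scheduled visit, with the rest uniform over Days 2-80. The share left out is (1 - q) x 44/79.

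| q (assumed) | Share left out |
|---|---|
| 0% | 55.7% |
| 25% | 41.8% |
| 50% | 27.8% |
| 75% | 13.9% |
| 100% | 0% |

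With q = 0, weighting ET days linearly towards early days gives 56.8%, and towards late days 54.6%. Coincidence with scheduled visits matters far more than the shape.

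**5. Illustrative counts.** The upper end is 260 x ET rate x 44/79, taking every terminating subject to supply an ET CMAI. The lower end is zero.
- 10% ET (26 subjects): 0 to about 14 scores.
- 20% ET (52 subjects): 0 to about 29.
- 30% ET (78 subjects): 0 to about 43.

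**6. Two single cases.** An ET CMAI on Day 35 falls in Days 32-38 and is labelled Week 5; the subject's Week 2 and Week 4 scores stay in the model. A subject whose only post-baseline CMAI is an ET score on Day 9 is labelled Week 1. That subject meets the Efficacy Sample definition but gives the MMRM no record.

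**The case against.** **Redaction.** Text is blacked out straight after the last-observation rule in SAP 10.1, under the window table (including the footnote to Week 12), in SAP 5.2 after the observed-case definition, at the end of 8.1.1 and throughout 8.1.2. An ET rule could be in any of these places. This stands: the point is conditional on the visible text, and the plan cannot be said to lack such a rule.

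**Size.** A reader might infer that half of all ET scores are lost. The documents do not support that, because the figure needs ET days spread evenly and away from scheduled visits. Protocol 3.7.1.4 also asks for ET evaluations only if possible, so not every withdrawal yields a score. Even the upper counts above, about 14 to 43, are 0.9% to 2.8% of 260 x 6 = 1,560 scheduled post-baseline CMAI records. This stands as a limit on size, although these are the records closest to dropout.

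**Consequence.** A reader might also infer that subjects are dropped or that the treatment effect is biased in a known direction. Neither follows. Earlier even-week scores remain, and no direction can be derived. Protocol 7.4.1 promises sensitivity analyses under missing not at random, whose details in SAP 8.1.3 are redacted.

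**Endpoint wording.** Protocol 3.5.1 says "The primary efficacy variable is the change from baseline to Week 12/ET in the CMAI total score", which might suggest that the ET score should stand in for Week 12. Protocol 7.4.1 and SAP 8.1 both place the outcome at the Week 12 visit, and the analysis imputes nothing, so that reading fails.

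**Contiguous windows.** Widening the even-week windows until they meet midway between visits looks like a natural repair. With the last-observation rule, however, an ET score on Days 18-21, 32-35, 46-49, 60-63 or 74-77 would overwrite the on-schedule score. That is 20 of the 35 odd-week days after Day 10, so this option should not be used.

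**Conclusion.** The point holds in conditional form. The visible rule gives an odd-window ET score a week that the primary and key secondary models do not contain, so a required pre-dropout score is left out. The routing needs no assumption beyond the visible text. The size does: 50% to 56% of ET scores if ET days are evenly spread before Week 12, falling to none if withdrawals coincide with scheduled visits. Usually only the ET score is lost. The exception is the subject with no other post-baseline CMAI, who is counted in the Efficacy Sample without contributing to the model. The point lapses if the redacted text already assigns these scores to a modelled week.

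**What to change.** First check whether the redacted text already assigns ET assessments. If it does not, add one sentence to SAP 10.1 before unblinding: for CMAI and CGI-S, an ET score that falls in an odd-week window is assigned to the next scheduled efficacy visit (Week 2, 4, 6, 8, 10 or 12). The subject has left by then, so the score never replaces an on-schedule one. None of the 79 days from Day 2 to Day 80 would then fall outside the model.

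The cost is wording and programming. The downside is a gap between the ET day and the nominal day. From Day 18 on, the gap is at most 10 days (for example 28 - 18 = 10, or 84 - 74 = 10). For Days 2-10 it is up to 14 - 2 = 12 days, and there the two-week CMAI recall partly covers behaviour before treatment.
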